#### 4.17.4 Radiological Objective Response Rate (Cohort B)

Radiological ORR is defined as the percentage of participants who have a confirmed investigator assessed response of CR or PR in their soft tissue disease assessed by RECIST 1.1 and bone scan status of non-PD or NE for their bone disease assessed by PCWG-3, and will be based on the molecularly eligible centrally confirmed evaluable for response set as well as evaluable for response set, and on a subset of participants with measurable disease in the molecularly eligible centrally confirmed evaluable for response set.

A confirmed response of CR/PR means that a response of CR/PR is recorded at 1 visit and confirmed by repeat imaging not less than 4 weeks after the visit when the response was first observed with no evidence of progression between the initial and CR/PR confirmation visit.

Data obtained up until progression, or last evaluable assessment in the absence of progression, will be included in the assessment of rORR. Participants who discontinue study treatment without progression, receive a subsequent anti-cancer therapy and then respond will not be included as responders in the rORR (i.e. both visits contributing to a response must be prior to subsequent therapy for the participant to be considered as a responder).

In the case where a participant has two non-consecutive visit responses of PR, then, as long as the time between the 2 visits of PR is greater than 4 weeks and there is no PD between the PR visits, the participant will be defined as a responder. Similarly, if a participant has visit responses of CR, NE, CR, then, as long as the time between the 2 visits of CR is greater than 4 weeks, then a best response of CR will be assigned.

The rORR will be based on the investigator RECIST data and using all scans regardless of whether they were scheduled or not.

Summaries will be produced that present the number and percentage of participants with a tumour response (CR/PR) based upon the number of participants with measurable disease at baseline per site investigator. A two-sided 80% confidence interval using Clopper-Pearson method will also be computed.

#### **4.17.5 Duration of rORR (Cohort B)**

The duration of radiological objective response is defined as the time from the date of first documented radiological response until date of objective radiologic disease progression or death. Descriptive data will be provided for the duration of response in responding participants, including the associated Kaplan-Meier estimate of median duration of response, where there are sufficient number of responders in the efficacy datasets as specified in [Table 6](#). A Kaplan-Meier plot and a swimmer plot will also be provided.

#### **4.17.6 Percentage of CTC count conversion from unfavourable to favourable (Cohort B)**

Conversion of CTC count is defined as a change from unfavourable at baseline ( $CTC \geq 5/7.5$  mL blood) to favourable at post-baseline ( $CTC < 5/7.5$  mL blood). Post-baseline result will be confirmed with a second consecutive value obtained three or more weeks later prior to radiological progression. Participants who discontinue study treatment without progression, receive a subsequent anti-cancer therapy and then respond will not be included as responders. The percentage of participants with CTC count conversion will be presented on those with unfavourable CTC at baseline. Summaries will be produced that present the number and percentage of participants with a CTC conversion for molecularly eligible and centrally confirmed evaluable for response set and evaluable for response set. A two-sided 80% confidence interval using Clopper-Pearson method will also be computed.

**4.17.7 Confirmed PSA decline (Cohort B)**

Confirmed PSA decline is defined as a PSA reduction greater than 50% from baseline which is confirmed later by a second consecutive measurement done at least three weeks later prior to radiological progression. Participants who discontinue study treatment without progression, receive a subsequent anti-cancer therapy and then respond will not be included as responders. The proportion of participants with confirmed PSA decline will be presented on the molecularly eligible and centrally confirmed set and safety analysis set. Summaries will be produced with the number and percentage of participants with confirmed PSA decline at DCO and a two-sided 80% confidence interval using Clopper-Pearson method.

**4.17.8 rPFS (Cohort B)**

Radiological PFS is defined as the time from the start of treatment until the date of objective radiographic disease progression or death. Participants who have not progressed (i.e., who have a CR, PR or SD by RECIST 1.1, and nonprogressive disease by PCWG-3) at the time of analysis will be censored, the latest date of their last evaluable RECIST 1.1 assessment or bone scan assessment that showed fewer than 2 new lesions. However, if the 2 or more consecutive scheduled radiographic assessments immediately prior to progression or death were missing, the participant will be censored at the time of the latest evaluable RECIST 1.1 and bone scan assessment prior to the 2 or more missed assessments. If the participant has no evaluable visits or does not have baseline data, they will be censored at Day 1 unless they die within 2 visits of baseline (in which case the participant’s date of death will be used). The rPFS time will always be derived based on scan/assessment dates, not visit dates. When the investigator is in doubt as to whether progressive disease has occurred and therefore reassesses the participant at a later date, the date of the initial scan should be declared as the date of progression if the repeat scans confirm progression. Analyses of rPFS will be based upon the molecularly eligible and centrally confirmed set and safety analysis set. KM plots of rPFS will be presented. Summaries will include the median rPFS with respective 80% CIs calculated using the Kaplan-Meier technique. Summaries will also provide the number and percentage of participants experiencing a rPFS event, and the type of event (radiological progression or death), along with the proportion of the participants alive and progression free at three months, six months, nine months and twelve months using KM technique. A 80% confidence interval for the survival estimates will be provided.

**4.18 Exploratory endpoints**

**4.18.1** CCI [Redacted]

CCI [Redacted].

**4.18.2** CCI [Redacted]

CCI [Redacted]  
CCI [Redacted]  
CCI [Redacted]

CCI [Redacted]  
CCI [Redacted]  
CCI [Redacted]

4.18.3 CCI [Redacted]

CCI [Redacted]  
CCI [Redacted]  
CCI [Redacted]  
CCI [Redacted]  
CCI [Redacted]  
CCI [Redacted]  
CCI [Redacted]  
CCI [Redacted]  
CCI [Redacted]

CCI [Redacted]

CCI [Redacted]  
CCI [Redacted]  
CCI [Redacted]  
CCI [Redacted]

CCI [Redacted]

CCI [Redacted]  
CCI [Redacted]  
CCI [Redacted]  
CCI [Redacted]

CCI [Redacted]

CCI [Redacted]  
CCI [Redacted]  
CCI [Redacted]  
CCI [Redacted]

CCI [Redacted]

CCI [Redacted]  
CCI [Redacted]  
CCI [Redacted]

4.18.4 CCI [Redacted]

CCI [Redacted]

2. Total treatment duration (if IP discontinued after the last dose > 0 mg) = (min(last dose date where dose > 0 mg, date of death, date of DCO) – date of first dose +1).

Since the planned schedule is to take ceralasertib continuously for the first 14 days in the cycle, Z=14

Actual treatment duration = total treatment duration – total duration of dose interruptions not in accordance with the protocol, and any planned no dose periods.

where total treatment duration will be calculated as above, and a dose interruption not in accordance with the protocol is defined as number of days where the participant has not taken any planned dose, due to toxicity or participant miss/forget to take the treatment dose. The treatment duration calculation makes no adjustment for any dose reductions that may have occurred.

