**Figure 1: Study design - Cohort A**

Protocol amendment 3

All aST, excluding participants with NSCLC and prostate cancer.

[figure not shown]
Ceralasertib administered twice a day between Days 1 to 14 in 28 day cycles.

Abbreviations: ATM=ataxia telangiectasia mutated; BID=twice daily; IHC=immunohistochemistry; NSCLC=non-small-cell lung carcinoma.

**Cohort B** is recruiting participants with ATM altered mCRPC (metastatic castration-resistant prostate cancer). Approximately 27 molecularly eligible and centrally confirmed participants will be enrolled into Cohort B. Unfavourable CTC count requirement may be introduced for all participants to ensure adequate (approximately  $\geq 50\%$ ) number of participants with CTC count  $\geq 5/7.5$  mL blood. Cohort B may be further expanded, CCI [REDACTED]. This would occur in the event an efficacy signal is observed, and subject to a protocol amendment. Refer to [Figure 2](#) for Module 1 Cohort B study design.

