## 4.6 Study Participants

### 4.6.1 Disposition of Participants

Disposition of all participants who enter the study will be summarised for all enrolled participants. The number and percentages of participants will be presented for the following categories:

- Enrolled (including the screen failures)

- Participants assigned to treatment
- Participants not assigned to study treatment (and reason)
- Received study treatment
- Did not receive study treatment (and reason)
- Participants ongoing with study treatment at data cut off (DCO)
- Participants ongoing in the study at DCO.
- Discontinued from study treatment (and reason)
- Prematurely withdrawn from study (and reason)

Additional listings and summaries on participants affected by the COVID-19 pandemic will also be presented as per standards.

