### ***Irradiated lesions/lesion intervention***

Previously irradiated lesions (i.e. lesion irradiated prior to entry into the study) should be recorded as NTLs and should not form part of the TL assessment.

Any TL (including lymph nodes), which has had intervention during the study (for example, irradiation / palliative surgery / embolisation), should be handled in the following way and once a lesion has had intervention then it should be treated as having intervention for the remainder of the study noting that an intervention will most likely shrink the size of tumours:

- Step 1: the diameters of the TLs (including the lesions that have had intervention) will be summed and the calculation will be performed in the usual manner. If the visit response is PD this will remain as a valid response category.
- Step 2: If there was no evidence of progression after step 1, treat the lesion diameter (for those lesions with intervention) as missing and if  $\leq 1/3$  of the TLs have missing measurements then scale up as described in the 'Scaling' section below. If the scaling results in a visit response of PD then the participant would be assigned a TL response of PD.
- Step 3: If, after both steps, PD has not been assigned, then, if appropriate (i.e., if  $\leq 1/3$  of the TLs have missing measurements), the scaled sum of diameters calculated in step 2 should be used, and PR or SD then assigned as the visit response. Participants with intervention are evaluable for CR as long as all non-intervened lesions are 0 (or  $<10$  mm for lymph nodes) and the lesions that have been subject to intervention have a value of 0 (or  $<10$  mm for lymph nodes) recorded. If scaling up is not appropriate due to too few non-missing measurements, then the visit response will be set as NE.

At subsequent visits the above steps will be repeated to determine the TL and overall visit response. When calculating the previous minimum, lesions with intervention should be treated as missing and scaled up (as per step 2 above).

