#### **4.19.1.2 Relative dose intensity**

Relative dose intensity (RDI) will be calculated as appropriate. RDI is the percentage of the actual dose delivered relative to the intended dose through to treatment discontinuation and is helpful to summarise dose reductions. Relative dose intensity will be defined as follows:

$$\text{RDI}(\%) = d/D \times 100 \text{ where}$$

- d is the actual cumulative dose delivered up to the actual last day of dosing.
- D is the intended cumulative dose up to the actual last day of dosing. D is the total dose that would have been delivered if there were no modification to dose or schedule.

Duration of dose delays will be derived for doses indicated as being delayed on the eCRF. For each individual dose, the duration of dose delay is the number of days the dose was received outside of the original planned dosing schedule. Overall duration of dose delays will be calculated as the sum of all individual dose delays during the study. For example, assume the eCRF indicate that there was a treatment delay (question “Treatment delayed” indicated as “Y” by investigator) then the duration of the individual delay will be [date first dose received after delay – date last dose received before delay +1].

If a participant permanently discontinues study treatment, then the date of last administration of study medication recorded on eCRF will be used to program the RDI. If a participant permanently

discontinues study treatment during a treatment interruption, then the date of last administration of study medication recorded on discontinuation form will be used to program the RDI.

The actual treatment duration, total treatment duration and RDI will be summarised. Exposure swimmer plot will be produced, with a line presented for each participant to display relevant exposure and disposition details.

In addition, the number and percentage of participants who received the planned starting dose of ceralasertib, with no interruption, with dose interruption, dose reduction and cycle delay will be presented. Reason for dose interruption, dose reduction and cycle delay will also be summarised and listed.

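### Actual treatment duration counts a planned dosing day with no dose as treated unless the reason is toxicity or a missed or forgotten dose

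*SAP*

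**What the plan says.** The derivation stands in the exposure text just before the paragraph on missed or forgotten doses. The revision history suggests that this is section 4.19.1.1, but its heading and opening are not visible.

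- Where treatment has been discontinued, total treatment duration runs from the first dose to the earliest of the last dose above 0 mg, death and data cut-off, plus one day.
- Actual treatment duration is that total minus "total duration of dose interruptions not in accordance with the protocol, and any planned no dose periods".
- An interruption of the first kind is a count of days on which "the participant has not taken any planned dose, due to toxicity or participant miss/forget to take the treatment dose".
- On the schedule: "Since the planned schedule is to take ceralasertib continuously for the first 14 days in the cycle, Z=14". The footnote to Figure 1 gives the cycle: "Ceralasertib administered twice a day between Days 1 to 14 in 28 day cycles".

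The next paragraph puts missed and forgotten doses together, records both under one reason (that the subject forgot the dose), and has them enter the derivation of actual exposure.

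Section 4.19.1.2 defines relative dose intensity (RDI) from the cumulative dose actually delivered. It has actual duration, total duration and RDI summarised, and adds: "Reason for dose interruption, dose reduction and cycle delay will also be summarised and listed".

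**The concern.** Actual treatment duration is meant to show how long participants were really on drug. Whether a day belongs in that count should depend on whether a dose was taken, not on why it was not. The definition names two causes, with no words such as for example or other reasons. A planned dosing day left undosed for a third cause is therefore neither a subtracted interruption nor a planned off-drug day, and it remains as treated time.

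The SAP gives some ground to expect such days. The overall adverse event table in section 4.19.2 has a row for any event leading to dose interruption, with no causality limit, while other rows are restricted to events related to treatment. An interruption for an event unrelated to the drug is not naturally called toxicity. Section 4.6.2 also lists more than 28 days of drug interruption as a deviation, again without limiting the cause.

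At stake is the accuracy of one reported exposure summary, in cohorts of about 25 and 27 participants where a few cases can move it.

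**Working it through.** The SAP gives no figure to reproduce, so the stated formula is applied to assumed participants.

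**Inputs from the SAP:** 14 dosing days per 28-day cycle; total duration = last dose date − first dose date + 1; actual duration = total − interruptions as defined − planned off-drug days.

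**Assumptions:** *c* cycles, none delayed; treatment discontinued, with the last dose on day 14 of the final cycle; *k* planned dosing days without a dose, all before that last dose, for a reason other than toxicity or a missed or forgotten dose; full dose on the days taken.

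**Formulas:**
- Total = 28(*c* − 1) + 14
- Planned off-drug days = 14(*c* − 1)
- Literal rule: total − off-drug days = 14*c*
- Days dosed: 14*c* − *k*
- Relative overstatement: 14*c* / (14*c* − *k*) − 1

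**Worked case,** *c* = 3 and *k* = 7: total = 28 × 2 + 14 = 70; off-drug days = 28. The literal rule gives 70 − 28 = 42. Days dosed are 70 − 28 − 7 = 35. 42/35 = 1.20, so 20% over.

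| Cycles | Literal rule (days) | Dosed, *k* = 3 | Over | Dosed, *k* = 7 | Over |
|---|---|---|---|---|---|
| 1 | 14 | 11 | 27.3% | 7 | 100.0% |
| 2 | 28 | 25 | 12.0% | 21 | 33.3% |
| 3 | 42 | 39 | 7.7% | 35 | 20.0% |
| 6 | 84 | 81 | 3.7% | 77 | 9.1% |

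The absolute excess is always *k* days; only the percentage shrinks with time on treatment. The one-cycle row holds only if dosing resumes and reaches day 14. If the participant simply stops, the last-dose-date rule already removes the undosed days.

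**Dependence on the coded reason,** *c* = 3 and *k* = 7: if the 7 days are coded as toxicity or forgotten, actual duration is 35; with any other code it is 42. The dosing is identical. RDI is 35/42 = 83.3% in both cases, because it uses the dose delivered.

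**Cycle delay:** an assumed 7-day delay before cycle 3, for another reason and with no other missed days, moves the last dose to day 77. The rule gives 77 − 28 = 49 against 42 dosing days, unless delay days count as a planned off-drug period. The visible text does not say.

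**The case against.** **Miss may be meant broadly.** If it covers any planned dose not taken, the gap closes. The wording allows this, but two things point the other way. The following paragraph ties missed to forgotten under a single recorded reason, and naming toxicity separately would add nothing if miss already covered everything. A hold ordered by the investigator is also not a participant missing a dose. At best the text is ambiguous, and two programmers could derive different values.

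**Part of the section is not visible.** The opening, the first case for total duration and the formula that uses Z are missing from the text at hand, and a wider definition could stand there. This lowers confidence. The visible definition is nevertheless a complete sentence.

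**Stronger readings that the SAP does not support.**
- A reader might infer that the plan foresees drug holds for procedures or the pandemic. Section 4.9.1 mentions interventions on target lesions ("for example, irradiation / palliative surgery / embolisation"), but only for how those lesions are measured. Section 4.6.1 promises "Additional listings and summaries on participants affected by the COVID-19 pandemic will also be presented as per standards", with nothing on dosing. For dispensing errors, section 4.6.2 provides case-by-case handling, including in the analysis where applicable.
- A reader might infer that drug delivered is overstated. The variable counts days and by its own terms ignores dose reductions; RDI measures drug delivered and is unaffected.
- A reader might treat a difference from RDI as an error. The two measures differ by design, and any dose reduction already separates them.
- A reader might infer distorted adverse event rates. Section 4.19.2 reports numbers and percentages of participants in the safety set and describes no exposure-adjusted rate.
- A reader might infer that nothing else is subtracted. Planned off-drug periods are.

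**Conclusion.** The point holds in a limited form. As written, a planned dosing day without a dose is counted as treated unless the recorded reason is toxicity or a missed or forgotten dose, so the result depends on reason coding as well as on dosing. The overstatement equals the number of such days before the last dose: for 3 to 7 days, about 8% to 20% over 3 cycles and 4% to 9% over 6. These figures rest on assumed participants, and the SAP does not give the number affected.

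The consequence stops at a descriptive summary of days on treatment. RDI, the adverse event percentages and the efficacy endpoints do not use this quantity. Severity is minor. Confidence is moderate, because the conclusion rests on the narrow reading of miss and on a section that is only partly visible.

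**What to change.** Define the subtracted days as every planned dosing day, up to the last dose, on which no dose was taken, whatever the reason, in addition to the planned off-drug periods. Drop the restriction to two causes. State in the same place whether days of cycle delay count as a planned off-drug period. Reasons need no place in the derivation, because section 4.19.1.2 already has them summarised and listed separately.

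The cost is a small wording change in the SAP and one condition in the exposure program. Reported actual durations may become slightly shorter. No dosing or other clinical rule changes.

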#### *Missed or forgotten doses*

Missed and forgotten doses should be recorded on the DOSE module as a dose interruption with the reason recorded as “Subject forgot to take dose”. These missed or forgotten doses will not be included as dose interruptions in the summary tables, but the information will appear in the listing for dosing. However, these missed and forgotten doses will be considered in the derivation of actual exposure.

#### *Participants who permanently discontinue during a dose interruption*

If a participant permanently discontinues study treatment during a dose interruption, then the date of last administration of study medication recorded on DOSDISC will be used in the programming.

#### **4.19.1.2 Relative dose intensity**

Relative dose intensity (RDI) will be calculated as appropriate. RDI is the percentage of the actual dose delivered relative to the intended dose through to treatment discontinuation and is helpful to summarise dose reductions. Relative dose intensity will be defined as follows:

$$\text{RDI}(\%) = d/D \times 100 \text{ where}$$

- d is the actual cumulative dose delivered up to the actual last day of dosing.
- D is the intended cumulative dose up to the actual last day of dosing. D is the total dose that would have been delivered if there were no modification to dose or schedule.

Duration of dose delays will be derived for doses indicated as being delayed on the eCRF. For each individual dose, the duration of dose delay is the number of days the dose was received outside of the original planned dosing schedule. Overall duration of dose delays will be calculated as the sum of all individual dose delays during the study. For example, assume the eCRF indicate that there was a treatment delay (question “Treatment delayed” indicated as “Y” by investigator) then the duration of the individual delay will be [date first dose received after delay – date last dose received before delay +1].

If a participant permanently discontinues study treatment, then the date of last administration of study medication recorded on eCRF will be used to program the RDI. If a participant permanently

discontinues study treatment during a treatment interruption, then the date of last administration of study medication recorded on discontinuation form will be used to program the RDI.

The actual treatment duration, total treatment duration and RDI will be summarised. Exposure swimmer plot will be produced, with a line presented for each participant to display relevant exposure and disposition details.

In addition, the number and percentage of participants who received the planned starting dose of ceralasertib, with no interruption, with dose interruption, dose reduction and cycle delay will be presented. Reason for dose interruption, dose reduction and cycle delay will also be summarised and listed.

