# Parexel International

AstraZeneca

D5339C00001

Statistical Analysis Plan

C1D8	Day 8	C1D1+7 ( $\pm 1$ ) days	C1D1+7 (-3/+2) days OR C1D5 to C1D10
C1D14	Day 14	C1D1+13 ( $\pm 2$ ) days	(C1D1+13) - 3 days to C2D1 - 2 days OR C1D11 to C2D1 - 2 days
C2D1 [b]	Day 29	C2D1 - 1 day to C2D1	C2D1 - 1 day to C2D1 + 3 days (C2D4)
C2D8	Day 36	C2D1+7 ( $\pm 1$ ) days	C2D1+7 (-3/+2) days OR C2D5 to C2D10
C2D14	Day 42	C2D1+13 ( $\pm 2$ ) days	(C2D1+13) - 3 days to (C3D1 -2) days OR C2D11 to C3D1 - 2 days
CxD1 [b],[c]	Day 1 + (x-1)*28 days	CxD1 - 1 day to CxD1	CxD1 - 1 day to CxD1 + 3 days (CxD4)
IP DISC	-	IP Disc date +14 days	IP Disc date + 14 days
Safety follow-up	IP DISC + 30 ( $\pm 7$ ) days	IP Disc date + 14 days to IP Disc date + 37 days	IP Disc date + 14 days to IP Disc date + 37 days

[a] Any value up to Day 1 including pre-treatment time will be considered as baseline. The handling of duplicate baseline value will be explained in Section 4.2.

[b] The start date of dosing of each cycle (CxD1) should be taken from the exposure data.

[c]  $X \geq 3$ .

eCRF - electronic Case Report Form. IP DISC - Investigational Product discontinuation.

For summaries showing the maximum or minimum values, the maximum/minimum value recorded on treatment will be used (regardless of where it falls in an interval and if it was collected at a scheduled or unscheduled visit).

Listings will display all values contributing to a time point for a participant; they will also highlight the value for the participants that will be used in the summary table, wherever possible.

RECIST and bone lesion (for cohort B only) assessments for all participants will be assessed every 8 weeks ( $\pm 7$  days) after Cycle 1 day 1 for the first year and every 12 weeks ( $\pm 7$  days) thereafter until objective disease progression by RECIST 1.1 (for cohort A) or radiological progression (for cohort B). Analysis visit windows will be assigned to the RECIST (cohort A) / radiological (cohort B) overall visit response assessments so that all assessments are allocated to the nearest scheduled time point. If more than one assessment falls in a given visit window, then the value closest to the protocol scheduled time point will be used. In the event of an equidistant time point, the earlier time point will be used.

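### The dose-delay formula in SAP Section 4.19.1.2 contradicts the definition beside it: a cycle started 7 days late is derived as 23 days

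*SAP*

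**What the plan says.** Section 4.19.1.2 says when a delay is derived: "Duration of dose delays will be derived for doses indicated as being delayed on the eCRF". It then defines the quantity for each dose: "the duration of dose delay is the number of days the dose was received outside of the original planned dosing schedule". Individual delays are added up: "Overall duration of dose delays will be calculated as the sum of all individual dose delays during the study". An illustration follows for a case where the investigator has ticked the delay question on the eCRF: "the duration of the individual delay will be [date first dose received after delay – date last dose received before delay +1". This is the only rule that a programmer is given.

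The schedule is fixed elsewhere in the SAP. The Figure 1 footnote in Section 3.1.1 says "Ceralasertib administered twice a day between Days 1 to 14 in 28 day cycles". The exposure derivation shortly before Section 4.19.1.2 says "Since the planned schedule is to take ceralasertib continuously for the first 14 days in the cycle, Z=14". Table 2 in Section 4.3.2 gives the target day for the first day of cycle x, from Cycle 3 on, as "Day 1 + (x-1)*28 days", and puts Cycle 2 Day 1 at Day 29.

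On reporting, Section 4.19.1.2 states: "The actual treatment duration, total treatment duration and RDI will be summarised". It adds counts and reasons for interruption, reduction and cycle delay. It does not list the length of a delay among the summaries.

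**The concern.** The definition measures lateness against a planned date. The formula measures the distance between two doses actually taken, counting both end dates. Under continuous dosing the two would differ by a small constant. On a schedule with 14 planned days off in every cycle they are different quantities, because the formula treats the planned rest as delay.

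Anyone programming from the formula would get a wrong value for every flagged cycle delay, and the excess would accumulate in the overall duration. Wherever the variable was shown, disruption of treatment would look much greater than it was.

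There is a second gap. The section refers to the original schedule but does not say whether a later cycle is measured against a fixed calendar from Cycle 1 or against the start of the previous cycle. This matters because the delays are summed.

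**Working it through.** **Inputs from the SAP**
- Dosing on Days 1 to 14 of 28, so the last planned dose of Cycle 1 falls on Day 14 (Figure 1 footnote; exposure derivation).
- Cycle 2 planned on Day 29 (Table 2).
- Definition, formula and summation rule from Section 4.19.1.2.

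**Assumption.** The SAP gives no numerical example of a delay, so there is no figure of its own to reproduce. The length k of the delay is illustrative. It was checked from 0 to 28 days.

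**One late cycle.** Let L be the last dosing day of the first block, and let Cycle 2 start on Day 29 + k.
- Definition: (29 + k) - 29 = k
- Formula: (29 + k) - L + 1 = k + 30 - L

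With L = 14 the formula returns k + 16, that is, 14 planned days off plus the two dosing dates:

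| Start of Cycle 2 | Definition | Formula |
|---|---|---|
| Day 29 (on time) | 0 | 29 - 14 + 1 = 16 |
| Day 30 | 1 | 30 - 14 + 1 = 17 |
| Day 36 | 7 | 36 - 14 + 1 = 23 |
| Day 43 | 14 | 43 - 14 + 1 = 30 |
| Day 57 | 28 | 57 - 14 + 1 = 44 |

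The on-time row only shows the offset, since delays are derived for flagged doses alone.

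If the block stopped early, the excess grows. For a 7-day delay:
- L = 13: 36 - 13 + 1 = 24, excess 17
- L = 10: 36 - 10 + 1 = 27, excess 20

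**Other readings of the formula**
- Attach the +1 to the last-dose date: 36 - (14 + 1) = 21. This is still not 7.
- Apply the formula to a gap inside the 14-day block, with the last dose on Day 5 and the next on Day 9. Days 6 to 8 are missed, so the definition gives 9 - 6 = 3 and the formula gives 9 - 5 + 1 = 5, an excess of 2. Here the alternative reading gives 9 - (5 + 1) = 3, which agrees, but the same reading fails for a late cycle.

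**Summing over cycles.** Suppose three successive cycles each start 35 days after the one before, with full blocks. Starts fall on Days 1, 36, 71 and 106, and the last doses before each delay on Days 14, 49 and 84.
- Formula: (36 - 14 + 1) + (71 - 49 + 1) + (106 - 84 + 1) = 23 + 23 + 23 = 69
- Definition, planned date = previous start + 28: (36 - 29) + (71 - 64) + (106 - 99) = 7 + 7 + 7 = 21. Excess 69 - 21 = 48.
- Definition, planned date = fixed calendar of Table 2: (36 - 29) + (71 - 57) + (106 - 85) = 7 + 14 + 21 = 42. Excess 69 - 42 = 27.

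The formula matches neither. The two reference dates also disagree with each other, because on the fixed calendar a delay carried into later cycles is counted again each time the values are added.

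**The case against.** - **No listed output changes.** Relative dose intensity is a ratio of cumulative doses, and actual treatment duration removes the planned dose-free periods separately. The tables count delays and give reasons. Whether delay length is reported at all depends on the table specifications, which are a separate document. This stands, and it limits the importance of the point. It does not make the derivation right: the SAP says that both the individual and the overall duration will be derived.
- **The formula is only an example, and the general definition governs.** An example has to satisfy the definition it illustrates, and no other computing rule is given.
- **The formula may be meant for gaps within the dosing block, where the excess is 2 days rather than 16.** The text speaks of doses, and what the eCRF question captures cannot be seen here. It is fair to say that 16 applies to late cycle starts only. The formula is wrong under either use.
- **Part of the neighbouring exposure section is redacted.** Undisclosed text might deal with the days off. Nothing visible subtracts them from a delay, and the formula as printed is complete in itself.
- **Table 2 is a visit-window table, not a dosing-delay reference.** This is correct. It is used above only as the one place where planned cycle days are written out. The reference to the original schedule in Section 4.19.1.2 leans towards a fixed calendar, which is why the planned date has to be stated and the summation checked against it.

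**Conclusion.** The definition and the formula in Section 4.19.1.2 contradict each other. For a first late cycle after a block that ended on Day 14, the formula overstates the delay by 16 days whatever its true length: 7 days becomes 23 and 14 becomes 30. The excess is larger if dosing stopped before Day 14. For a gap within the block it is 2 days. In the three-cycle example the overall duration is 69 days, against 21 or 42 by the definition, depending on the planned date.

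The delay lengths are illustrative; the 16-day offset follows from the SAP's own schedule. The error is confined to the individual and overall delay durations. Efficacy, relative dose intensity, treatment duration, and the counts and reasons for cycle delay are untouched. It should be corrected before programming, but it does not threaten the trial's conclusions.

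**What to change.** Replace the formula with: cycle delay = actual start date of the delayed cycle minus planned start date of that cycle.

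State the planned date in the same sentence:
- If it is the previous cycle's start + 28 days, the individual delays can be summed as the SAP intends, and a carried-over delay is counted once (21 days in the example).
- If it is the fixed calendar from Cycle 1, the individual values should not be summed. In the example the last cycle's value, 106 - 85 = 21, already holds the accumulated delay.

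Say also that the rule applies to late cycle starts, and leave gaps within the 14-day block to the interruption derivation in the exposure text.

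The cost is one sentence in the SAP and one line of code. No new data are needed, since Table 2, footnote b, already takes cycle start dates from the exposure data. The change corrects a derivation only and implies nothing about dose or schedule.
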